3 INVESTIGATIONAL PLAN

3.1 Overview of Study Design

The purpose of this randomized blinded study is to evaluate whether oseltamivir modifies viral shedding in an ambulatory population with uncomplicated influenza. This study is also designed to explore the relationship between virologic effects and clinical effects, effects on pro-inflammatory mediators, and to start understanding if improvements to virologic shedding correlate with improvements in clinical outcomes. For this reason, the study is powered to show an anticipated difference in virologic shedding. This is a multicenter international study. Up to approximately 50 sites may participate in this protocol.

It is anticipated that about 800 subjects may be enrolled to allow 560 eligible subjects to be randomized in this study. The anticipated study duration is 7 years. The original sample size of the study was powered to show a difference in virologic shedding as detected by TCID₅₀ (as detailed in Section 9.2). With new virologic techniques such as PCR, it is anticipated that the objectives of this study may be achievable with smaller numbers of subjects; therefore the sample size has been reduced.

Subjects with an influenza-like illness will be screened for the study, and those found positive for influenza will be randomized in a 1:1 manner to receive a blinded study treatment consisting of either oseltamivir or placebo for 5 days. The study arms are as follows (Table 2):

Table 2: Treatment Allocation

| Arm | Drug | Allocation Ratio | Capsule |
|-----|---------------------|------------------|-------------|
| 1 | Oseltamivir | 1 | Oseltamivir |
| 2 | Oseltamivir placebo | 1 | Placebo |

Subjects will be assessed on Study Day 0 (pre-dose), and on Study Days 3, 7, and 28. All subjects will undergo a series of efficacy and safety assessments during the study. Blood samples will be collected on Days 0, 3, 7, and 28.

Table 4 in Section 6 presents the schedule of assessments. A detailed presentation of assessments to be conducted at each visit is presented in Section 6.3.

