9.1 General Considerations

All statistical inferences will be based on two-sided tests with an α -level of 0.05. Categorical data will be summarized by the number and percent of subjects falling within each category. Continuous variables will be summarized by descriptive statistics, including mean, standard deviation, minimum, maximum, median, and relevant percentiles. Time-to-event endpoints will be summarized by median durations, hazard ratios, and corresponding 95% confidence intervals. Study Day 0 will be defined as the day of randomization.

The Statistical Analysis Plan will provide the procedure for accounting for missing, unused, and spurious data.

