#### **4.9 Secondary Endpoints: Clinical Endpoints [DIARY1] (PEP and ITT)**

Many of the clinical endpoints rely on data collected on diary cards completed by the study participants. The subjects are asked to complete these twice a day (at 8AM and 8PM) on Days 0 through 14 and then again on Day 28. Fever is recorded for the preceding 12 hour period at both times each day, and symptoms are recorded at both times for Days 0 to 7 and then once daily on Days 8 to 14. Functional status (based on the Physical Function domain questions from the SF-36) and two questions giving a global assessment of status are completed daily at 8AM.

- a. Duration of clinical symptoms. Duration of clinical symptoms is defined as the time from Day 0 to the first of two successive measurements at which all clinical symptoms are grade 0 (absent) or 1 (mild). A measurement is considered to be the 8AM or 8PM assessment during Days 0 to 7 (so two measurements are obtained per day) and then the daily assessment thereafter. Time will then be calculated in half-days through to Day 7. For the purposes of defining the endpoint, if the subjects' first two assessments on (baseline assessment and first subsequent diary card assessment) satisfy this criterion, then the duration will be set to zero. Missing values will be ignored [this is equivalent to assuming that a missing value would have (a) indicated at least one grade 2+ symptom if the preceding record includes a grade 2+ symptom or if the first Day 0 value is missing; (b) indicated no grade 2+ symptoms if the preceding and succeeding assessments show no grade 2+ symptoms; and (c) indicated a grade 2+ symptom if the preceding assessment shows no grade 2+ symptom and the succeeding value shows a grade 2+ symptom]. Times will be considered as discrete (i.e. based on the schedule of completion of diary cards) and subjects not having two succeeding assessments with only grade 0 or 1 symptoms at any time during follow-up will be censored immediately after Day 14 (the last scheduled measurement time on which an endpoint can occur).
- Kaplan-Meier plot (and associated table) of the percent of subjects without clinical symptoms per the above definition over time, with the median duration of time to alleviation of such symptoms and its 95% confidence interval.
  - P-value comparing randomized arms from the log rank test.

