  - Sensitivity analyses assuming (a) that missing values would include grade 2+ symptoms, (b) that missing values would not include grade 2+ symptoms, (c) that missing values would include grade 2+ symptoms in one randomized arm and would not include grade 2+ symptoms in the other arm (so as to maximize the difference between arms), and (d) the opposite of (c) (so as to minimize the difference between arms).

Note: Secondary analyses restricting to those with at least one grade 2 (moderate) or grade 3 (severe) clinical symptom based on the Diary Card at randomization, will be conducted for section a described above.

- b. Absence of fever Time to the absence of fever is defined as the time from Day 0 to the first of two successive assessments (through to Day 7) or the first assessment (Day 8 to Day 28) at which no fever  $\geq 38.0^{\circ}\text{C}$  is reported during the prior 12 hours and no antipyretics have been taken during the 24 hours. Time will then be calculated in half-days through to Day 7. For the purposes of defining the endpoint, if the first two assessments on Day 0 or 1 satisfy this criterion, then the duration will be set to zero. Missing values will be ignored [this is equivalent to assuming that a missing value would have (a) indicated fever if the preceding record includes fever or if the first Day 0 value is missing; (b) indicated no fever

if the preceding and succeeding assessments show no fever; and (c) indicated fever if the preceding assessment shows no fever and the succeeding value shows fever]. Times will be considered as discrete (i.e. based on the schedule of completion of diary cards) and subjects not having a 24-hour period without fever at any time during follow-up will be censored immediately after Day 14 (the last scheduled measurement time on which an endpoint can occur).

- Analysis for duration of fever will follow the same approach as for duration of clinical symptoms.
- c. Resolution of Symptoms and Fever. Time to resolution of all symptoms AND Fever is defined as the time from Day 0 to the first of two successive measurements at which all clinical symptoms are grade 0 (absent) or 1 (mild) and no fever  $\geq 38.0^{\circ}\text{C}$  is reported during the prior 12 hours and no antipyretics have been taken during the 24 hours.
- Analysis for duration of clinical symptoms and fever will follow the same approach as for duration of clinical symptoms.

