- d. Global assessment: Times to “feeling as good as you did before you had the flu” and “functioning as well as you did before you had the flu” will be defined as the times of two successive measurements with “yes” responses to the respective global assessment questions.
- The details of the definition, handling of missing values and analysis will follow that for duration of clinical symptoms.
- e. Functional status: This is assessed using the 10-item domain of Physical Function from the SF-36, and calculated as the average of the scores of all 10 items. Functional status is evaluated daily through to Day 14 and then at Day 28.
- Scoring, including handling of missing values, will be undertaken per the standard instructions for the RAND 36-Item Health Survey 1.0 instrument (located at: [http://www.rand.org/health/surveys\\_tools/mos/mos\\_core\\_36item\\_scoring.htm](http://www.rand.org/health/surveys_tools/mos/mos_core_36item_scoring.htm) 1). If all 10 components are not scored, the pre-illness functional status will be scored as missing.
  - Figure and associated Table: Median, 25th and 75th percentiles, (and min and max value in table), with sample size, at each required measurement time.
  - Figure and associated Table: Median, 25th and 75th percentiles, (and min and max value in table), with sample size, change from Day 0 at each required measurement time.

- Statistical comparison between randomized arms of changes in score will be undertaken at Days 3, 7, 14 and 28 using Wilcoxon's test.
  - Time to return of physical function to pre-illness level is defined as the time from Day 0 to the first of two successive measurements at which the physical function score equals or is better than the pre-illness score (obtained by recall at enrollment). Time will be calculated in daily increments through to Day 14. For the purposes of defining the endpoint, if a subject's Day 0 and Day 1 assessments satisfy this criterion, then the duration will be set to zero. Missing values will be ignored. Times will be considered as discrete (i.e. based on the schedule of completion of diary cards) and subjects not having two successive assessments with scores equal to or better than the pre-illness score will be censored immediately after Day 14 (the last scheduled measurement time on which an endpoint can occur).

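### SAP 4.9a–e omits the hazard ratios with 95% confidence intervals that Protocol 9.1 specifies, leaving the diary-based time-to-event endpoints without a between-arm effect estimate

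*SAP*

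**What the plan says.** Protocol 9.1 sets the general rule: "Time-to-event endpoints will be summarized by median durations, hazard ratios, and corresponding 95% confidence intervals".

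SAP 4.9a, on duration of clinical symptoms, plans a Kaplan-Meier plot and table "with the median duration of time to alleviation of such symptoms and its 95% confidence interval", then a "P-value comparing randomized arms from the log rank test". SAP sections 1 and 4 say results are shown by randomized arm, so the median and its interval are per-arm quantities.

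The later items inherit this:
- Item b: "Analysis for duration of fever will follow the same approach as for duration of clinical symptoms".
- Item c: "Analysis for duration of clinical symptoms and fever will follow the same approach as for duration of clinical symptoms".
- Item d, the two global questions: "The details of the definition, handling of missing values and analysis will follow that for duration of clinical symptoms".
- Item e, time to return of physical function, repeats the same plot, median and log-rank test in its own words.

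SAP 4.6c–d treats death differently. Besides a Kaplan-Meier plot and log-rank test, it gives 95% confidence intervals for the 28-day rates and for their difference between arms. SAP 4.6f applies the same approach to hospitalization.

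**The concern.** A log-rank p-value tests whether the curves differ. It does not say by how much, or which effect sizes the data exclude. Two medians with separate intervals do not fill the gap, because neither interval is for the difference.

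This matters more than usual here. Protocol 3.1 says that "the study is powered to show an anticipated difference in virologic shedding", so the clinical comparisons were not what set the sample size and an inconclusive p-value is plausible. Without an interval, a reader of such a result cannot tell whether a useful benefit has been ruled out or merely not shown. Protocol 1.2 and 3.1 also make the relation between virologic and clinical improvement part of the rationale. The analysis of that association is deferred to a later plan (SAP 4.9.1), but interpreting it will still call for the size of the clinical effect.

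There is also an internal consequence. The missing-data sensitivity analyses in SAP 4.9a include scenarios built to make the difference between arms as large and as small as possible, yet the section defines no measure of that difference. Only p-values could be compared formally across the scenarios.

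**Working it through.** **1. What each item provides between arms**

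| SAP item | Endpoint | Between-arm output | Interval for the treatment effect |
|---|---|---|---|
| 4.8.1b | Day 3 detectable virus (primary) | 95% CI and p-value | Yes |
| 4.6c–d | Death to Day 28 | Log-rank p; difference in 28-day rates with CI | Yes, but no hazard ratio |
| 4.6f | Hospitalization | As for death | Yes, but no hazard ratio |
| 4.9a | Symptoms | Log-rank p | No |
| 4.9b, c | Fever; symptoms and fever | As 4.9a | No |
| 4.9d | Two global questions | As 4.9a | No |
| 4.9e | Return of physical function | Log-rank p | No |
| 4.9f | Complications | Comparison of arms, with a 95% CI for the percentage | Unclear whether per arm or for the difference |

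Six time-to-event endpoints in 4.9a–e have no interval for the treatment effect. Protocol 9.1 asks for one on each.

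**2. How wide the missing interval would be**

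The plan has no figure to reproduce. The sample sizes in Protocol 9.2 concern viral AUC and Day 3 detectability, and no event count or hazard ratio is given for these endpoints. The event total D is therefore an assumption.
- Lower value: 400 subjects × 0.85 with the event = 340. Both inputs are assumed.
- Upper value: 560, meaning every randomized subject has the event. SAP 4.8 includes the 50 pilot subjects in secondary analyses, so 560 is the ceiling.

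With 1:1 allocation, SE(log HR) ≈ √(4/D) = 2/√D, and the 95% limits are HR ÷ f and HR × f, where f = exp(1.96 × 2/√D).
- D = 340: SE = 0.1085; f = exp(0.2126) = 1.24.
- D = 428: SE = 0.0967; f = exp(0.1895) = 1.21.
- D = 560: SE = 0.0845; f = exp(0.1656) = 1.18.

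**3. What a borderline result would conceal**

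Take D = 428, chosen only as a value inside the range, and a two-sided p of 0.06 (z = 1.88).
- log HR ≈ 1.88 × 0.0967 = 0.182, so HR ≈ 1.20.
- 95% limits: exp(0.182 ± 0.1895) = 0.99 to 1.45.

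The data would be compatible both with essentially no effect and with a 45% higher rate of alleviation. SAP 4.9a as written would show p = 0.06, two curves and two medians, but not that interval.

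**4. Resolution of the medians**

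SAP 4.9a counts time in half-days through Day 7, so over that period medians move in steps of about 12 hours. Protocol 1.3.2 cites illness shortened by 29 and 31 hours at 75 mg bid in two earlier adult trials, that is 29/12 = 2.4 and 31/12 = 2.6 steps. Per-arm medians on that grid give no interval showing whether a benefit of that size is supported or excluded.

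**The case against.** Several points can be made for the plan as it stands.

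- **The protocol still binds.** Protocol 9 says the SAP adds detail, so 9.1 can be read as still requiring the hazard ratios. That is a fair reading, and a reader might wrongly infer that they were deliberately dropped. The SAP text reviewed neither withdraws nor explains them. Its contents list an introduction and a summary of key updates that were not available for this review, so an explanation there cannot be excluded. Even so, 4.9 is the list that will be programmed, and it contains no hazard ratio.
- **More than a p-value is planned.** This is correct. A reader might infer that a p-value is all these endpoints receive, but curves, tables, per-arm medians with intervals and sensitivity analyses are all specified. What is missing is the between-arm interval.
- **Other clinical endpoints do have intervals.** Also correct. A reader might infer that no clinical endpoint has an effect estimate with its uncertainty. SAP 4.6d–f contradicts that for mortality and hospitalization, and 4.9f plans some interval for complications.
- **A hazard ratio can be approximated from the p-value and event count**, as step 3 above does. This stands only in part. It relies on a large-sample formula that ignores heavy ties and durations set to zero, and readers should not have to back-calculate a promised result.
- **The event counts are not in the documents.** True. They are assumptions, used only to show scale.

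**Conclusion.** The mismatch is real and limited. Protocol 9.1 specifies hazard ratios with 95% confidence intervals for time-to-event endpoints, and SAP 4.9a–e lists none. Six diary-based secondary endpoints are left with per-arm medians and a log-rank p-value but no estimate of the treatment effect with an interval. Time to death and time to hospitalization also lack a hazard ratio, but their difference in 28-day rates has an interval, so the practical gap there is small.

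The textual finding needs no assumption beyond the SAP text available. The size does: with 340 to 560 events, 1:1 allocation and the usual approximation, the interval would extend by a factor of about 1.24 to 1.18 either side of the hazard ratio. The primary analysis already has a confidence interval and is unaffected.

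**What to change.** Add to SAP 4.9a, and carry to 4.9b–e: *hazard ratio (oseltamivir:placebo) with 95% confidence interval from a Cox model, with tie handling suited to the discrete assessment times*. Report it in the sensitivity analyses too, so that the scenarios can be compared on an effect scale.

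Optionally, add the difference in restricted mean time to Day 14 with its 95% confidence interval, in case hazards are not proportional. Protocol 9.1 does not require this.

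For death and hospitalization, either add the hazard ratio or state in SAP 4.6 that the difference in 28-day rates stands in its place. If hazard ratios were left out of 4.9 on purpose, say so and name the replacement estimate.

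The cost is a few lines of SAP text and code, using data already planned for collection. The change should be made before unblinding.

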9.2.1 Sample Size Re-estimation

After analysis of the pilot study data, the primary endpoint was chosen as the percentage of subjects shedding virus by PCR in NP swab at Day 3.

Assumptions:

- Pooled percentage of subjects with virus detectable by PCR at Day 3 combining both arms is 50% (based on pilot study data)
- Require 90% power to detect difference between arms using two-sided Fisher’s Exact Test with Type I error rate of 0.05.
- Proportion of participants with missing qPCR at Day 3 is 10% (due to losses to follow-up, sample handling and laboratory assay problems).

| Magnitude of difference in proportions between arms (proportions in the two randomized arms) | Sample size (combined across both arms) without adjustment for missing values | Sample size (combined across both arms) with adjustment for 10% with missing values & not accounting for the 50 subjects in the pilot study) |
|--|---|--|
| 25% (37.5% vs 62.5%) | 174 | 194 |
| 20% (40% vs 60%) | 280 | 312 |
| 15% (42.5% vs 57.5%) | 490 | 546 |

Table 9: Re-estimated Sample Size Under Different Treatment Effects

This sample size has been chosen to give approximately 90% power to detect an absolute difference of 15% in the proportion of subjects with undetectable virus shedding at Day 3 in NP swabs (e.g., a reduction of 15% from 57.5% in the oseltamivir arm to 42.5% in the placebo

arm). Less than a 15% absolute difference in viral shedding is unlikely to be viewed as clinically meaningful. Therefore, the revised sample size calculations confirm keeping the sample size 560 subjects, including 50 in the pilot study and 510 in the main study.

This power calculation is based on the fact that approximately 50% of subjects in the pilot study had undetectable virus in NP swabs at Day 3 (pooled over randomized arms) and included allowance for 10% of subjects to have unavailable viral shedding results at Day 3. The calculation assumed use of a t-test to compare proportions using a two-sided type I error rate of 0.05.

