##### **4.3.3 Disease and vaccination status (ITT)**

- a. Hours since onset of influenza-like illness to screening (as defined in protocol section 4.3, item 4) [SCRVIS3]

- b. Hours from screening to randomization
- c. Hours from randomization to treatment initiation [SDCOMP1]
- d. Influenza vaccination the season of (and anytime prior to) enrollment
- e. Vital signs: Blood pressure (diastolic and systolic), heart rate, mean arterial pressure, temperature [VITALS2]
- f. Smoking status (current, previous, never)
- g. Anthropometric measurements: weight, height, body mass index [VITALS2]
- h. SaO2 and SaO2 category (<93% vs. ≥93%) [VITALS2]
- i. Presence of fever (≥38°C) [DIARY1]
- j. Symptom score for each of the following symptoms (scored on a 4-point scale: 0=absent, 1=mild, 2=moderate, 3=severe) [DIARY1]
  - Cough
  - Nasal obstruction
  - Sore throat
  - Fatigue
  - Headache
  - Myalgia
  - Feverishness
  - Rhinorrhea
  - Nausea
  - Vomiting
  - Diarrhea
  - Other (as specified by study participant)
- k. Overall symptom score (defined as the sum of scores for the preceding list of symptoms)
- l. Functional status pre-illness (assessed using subjects pre-illness recall of the 10-item domain of Physical Function from the SF-36) [DIARY1]
- m. Functional status on Day 0 (assessed using the 10-item domain of Physical Function from the SF-36) [DIARY1]
- n. Presence of each of the following complications of influenza [EVENTS3]:
  - Sinusitis
  - Otitis media
  - Bronchitis / bronchiolitis
  - Pneumonia
  - Antibiotic use for reason other than above

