- g. AUCs will be calculated for the self-collected swabs. This is defined as the area below the line formed by joining the measured values at each successive scheduled measurement time and above the limit of detection. This will be calculated using the trapezoidal rule. Missing values will be ignored (this is equivalent to imputing a missing value using linear interpolation between the previous and succeeding available values). If the Day 0 value is missing, then the subject will be excluded from the analysis.
  - Figure and associated table showing number of subjects and minimum, maximum, median, 25% and 75% percentile of the value of viral shedding at each scheduled measurement time. This will be presented (a) imputing values

as defined above for the calculation of AUC, and (b) using observed values only.

- Table showing number of subjects and minimum, maximum, median, 25% and 75% percentile of the AUC, both over all subjects and by strata defined by quartile of Day 0 measurement.
- P-value comparing randomized arms from Wilcoxon rank sum test stratified by quartile of Day 0 measurement.

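### The log-rank tests of the clinical recovery times are valid, but they use neither the Day 0 severity already collected nor the randomization stratum, and so may give up power

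*SAP*

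**What the plan says.** SAP 4.9a analyses the duration of clinical symptoms by a Kaplan-Meier plot, a median with its confidence interval, and a "P-value comparing randomized arms from the log rank test". It names no stratum or covariate. Items b (fever), c (symptoms and fever) and d (two global questions) adopt the analysis of item a. Item e repeats the log-rank test for return to pre-illness physical function. Six recovery times are therefore tested without adjustment.

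The Day 0 data exist. SAP 4.3.3k derives an "Overall symptom score (defined as the sum of scores for the preceding list of symptoms"), and 4.3.3 also lists Day 0 fever (i), recalled pre-illness function (l) and Day 0 function (m). All appear only as baseline descriptions. The nearest step towards using severity is a note under item a: "Secondary analyses restricting to those with at least one grade 2 (moderate) or grade 3 (severe) clinical symptom based on the Diary Card at randomization".

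The SAP does stratify on a baseline value in one place, the self-swab AUC in 4.10g: "P-value comparing randomized arms from Wilcoxon rank sum test stratified by quartile of Day 0 measurement". Protocol 5.1 stratifies randomization by symptom duration (0–24 v 25–48 hours), but SAP 4.9 does not carry that factor into any test. Protocol 9.1 promises hazard ratios for time-to-event endpoints, and SAP 4.9 lists none.

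**The concern.** Part of each subject's distance from recovery is fixed at Day 0 by definition. In 4.9a a subject with nothing worse than mild symptoms at the first two assessments is given duration zero, while everyone else must bring every symptom down to absent or mild. Items b and e have matching set-to-zero rules for fever and physical function. Where a baseline value helps to determine the outcome, a test that ignores it leaves explainable variation in the comparison.

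The restriction to subjects with a grade 2 or 3 symptom does not fill the gap. It is written for item a only, it drops subjects, and it leaves severity among the remainder unaccounted for.

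What is at stake is power for the clinical endpoints. The trial sets out to relate virologic to clinical improvement, yet protocol 3.1 powers it on shedding alone and no power is stated for any clinical time. Choosing the adjustment in advance also avoids an argument after unblinding if Day 0 severity happens to differ between arms.

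**Working it through.** **1. The plan's own figure.** Protocol 9.2.1 ("Require 90% power to detect difference between arms") concerns Day 3 shedding only. At 245 per arm, 42.5% v 57.5%, two-sided 0.05, the exact power of Fisher's test is 0.903. Allowing for 10% missing, 245/0.9 = 272.2, so 273 per arm and 546 in total. Table 9's 490 and 546 reproduce. They say nothing about the clinical times.

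**2. Benchmark for the plain log-rank test.** From the documents: 1:1 allocation; two-sided 0.05 (protocol 9.1, "All statistical inferences will be based on two-sided tests"); 560 subjects, since SAP 4.8 keeps the pilot subjects in the secondary analyses. Protocol 9.5 would exclude those 50, which would lower the power of either test. Assumed: 10% loss, so 560 × 0.9 = 504, all with the event.

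Power = Φ(√(D/4) × ln HR − 1.96). For D = 504, √126 = 11.22. At HR 1.3: 11.22 × 0.262 = 2.945; less 1.96 = 0.985; power 83.8%. At HR 1.25 it is 70.7%, and at HR 1.2 it is 53.5%.

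**3. Simulation with the total spread of recovery times held fixed.** The diary grid comes from SAP 4.9: half-days to Day 7, daily to Day 14. All other inputs are assumed: 500 subjects, log-normal times with median 4 days and log-SD 0.8, treatment multiplying time by 0.83, 9,000 trials per row. Correlation is between Day 0 score and log recovery time.

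| Correlation | Plain | Stratified by quartile | Change (points) |
|---|---|---|---|
| 0 | 65.8% | 65.1% | −0.7 |
| 0.2 | 66.4% | 67.3% | +0.9 |
| 0.3 | 67.2% | 70.1% | +2.9 |
| 0.45 | 66.8% | 74.4% | +7.6 |
| 0.6 | 65.5% | 81.3% | +15.8 |

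Type I error, plain v stratified: 5.1% v 5.4% at correlation 0.3, and 4.6% v 4.5% at 0.6. A separate run on the same assumptions gave about 66% plain, against 67%, 68%, 75% and 82% stratified at 0.2, 0.3, 0.45 and 0.6.

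**4. Simulation with the hazard ratio within severity held fixed.** Assumed: 504 subjects, Weibull times (shape 1.3, median 4 days), a normally distributed Day 0 score acting on the log hazard, same grid, 3,000 trials per cell. Correlation is Spearman's, with the recorded time.

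| Correlation | HR 1.3: plain → stratified | HR 1.25: plain → stratified |
|---|---|---|
| 0 | 82.6% → 81.9% (−0.7) | 69.0% → 68.5% (−0.5) |
| 0.17 | 80.3% → 81.4% (+1.1) | 65.3% → 66.3% (+1.0) |
| 0.24 | 77.1% → 80.2% (+3.1) | 63.5% → 68.3% (+4.8) |
| 0.38 | 67.6% → 78.0% (+10.4) | 53.4% → 66.0% (+12.6) |
| 0.52 | 55.6% → 75.6% (+20.0) | 45.0% → 63.2% (+18.2) |
| 0.62 | 43.9% → 74.5% (+30.6) | 34.8% → 60.4% (+25.6) |

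Both tests had type I error between 4.0% and 6.0%. Gains exceed those in step 3 because here a stronger Day 0 effect adds spread to the recovery times and dilutes the unadjusted contrast. In step 3 it explains more of a fixed spread.

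**5. In subjects.** The equivalent increase in sample size is the squared ratio of (1.96 + z for power). At HR 1.3, correlation 0.24: (1.96 + 0.849)²/(1.96 + 0.742)² = 1.08, or 8% more subjects. At 0.38: (1.96 + 0.772)²/(1.96 + 0.457)² = 1.28, or 28% more.

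**6. What was not simulated.** The duration-zero group is barely represented: in step 3, Φ(ln(0.5/4)/0.8) = Φ(−2.60), about 0.5% of subjects, falls below half a day. Only quartile stratification on a generic score was run. The randomization stratum and the particular baselines for items b, d and e were not.

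**The case against.** The case against acting is substantial.

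- **The planned test is valid.** Its simulated type I error is near 5%, so chance imbalance in Day 0 severity is already covered. A reader might infer that the tests are biased or wrong. They are not.
- **No passage measures the prognostic value.** A reader might also infer that Day 0 score largely sets recovery time. The documents contain no correlation, hazard ratio or pilot result on this. The set-to-zero rules show that some dependence exists, not that it is strong. This objection stands, and it is why the gain can only be given as a range.
- **The summed score is an imperfect match to 4.9a.** Eleven mild symptoms sum to 11 and meet the criterion. One severe symptom sums to 3 and does not. This stands in part: the sum can misorder some subjects, which would weaken its correlation with recovery time.
- **The 4.10g precedent is limited.** The AUC is computed from the Day 0 value itself, which is not true of a recovery time, and the primary test in 4.8.1 is unadjusted. The precedent shows that the method is acceptable to the authors, not that it is required here.
- **These are secondary endpoints on which the trial is not powered, and item a already has a restricted analysis.** This limits the importance of the point but does not remove it. The restriction is not an adjustment, and the change costs almost nothing.

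**Conclusion.** The point holds as one of efficiency. All six tests in SAP 4.9a–e leave out Day 0 severity and the randomization stratum, although both are recorded before treatment starts.

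Under assumed correlations, quartile stratification loses at most 1 point of power if the score is uninformative. It gains about 1 to 5 points at correlations of 0.2 to 0.3, and roughly 15 points or more at 0.6. The upper figures depend on the model as well as on the correlation: +15.8 points in step 3 at 0.6, against +25.6 to +30.6 in step 4 at 0.62. Nothing in the documents says where in this range the trial lies. The case for the change is that the possible loss is trivial and the possible gain is not. It does not rest on any claim that the gain will be large.

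**What to change.** Before unblinding, specify in SAP 4.9 a log-rank test stratified by the randomization stratum (0–24 v 25–48 hours) and a Day 0 category matched to each endpoint:

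- **a, c and d:** category of the Day 0 overall symptom score (4.3.3k), for example quartiles of the pooled arms. The number of Day 0 symptoms at grade 2 or above, from the same diary entry, is an alternative closer to the definition in item a.
- **b:** Day 0 fever, <38.0 v ≥38.0 °C (4.3.3i).
- **e:** category of the Day 0 shortfall from the recalled pre-illness physical-function score (4.3.3l minus 4.3.3m). The endpoint is defined by that gap, not by the Day 0 score alone.

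Give subjects with a missing Day 0 value their own stratum, and keep the plain log-rank test as a sensitivity analysis. Two randomization strata by four quartiles make eight cells, averaging 504/8 = 63 subjects, which is workable.

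A Cox model with the same terms would supply the hazard ratios promised in protocol 9.1. The diary times are heavily tied, so name the method for ties. In the step 4 simulations a Cox Wald test with Breslow's approximation was conservative (type I error 2.9% to 3.9%), so the p-value is better taken from the stratified log-rank test.

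The cost is some SAP wording and a strata term per test, with a negligible loss of power if the baseline value proves not to be prognostic.
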